6.3. Handling of Missing Data

Subjects who withdraw from the study after the initiation of the study drug will not be replaced and available data for these subjects until the point of withdrawal will be summarized.

The missing baseline assessment will not be imputed.

For categorical variables with missing values, a category documenting the frequency of missing values will be displayed in the summary tables.

For I-GAIS, the LOCF will be used to impute the missing data at Day 90. For subjects who withdraw from study prior to Day 90, the last non missing assessment will be carried forward for Day 90 analysis (ie, LOCF Approach).

For Body Q- Appraisal of Cellulite, if missing data at a visit is less than 50% of the scale's items, the mean of the completed items multiplied by 11 will be used to determine total score. If the imputed value for total score is in decimals then the nearest integer will be considered to get the RASCH score, and the rounded value will be used for the summary and analysis. Also, if the missing data at a visit is more than 50% then for that subject raw sum score as well as transformed score will be considered as missing.

Subjects who withdraw early from study will be encouraged to have all Day 180 procedures and assessments completed at an early termination visit.

There will be no imputation of missing values for safety data, however missing relationship between AE and study drug will be considered as related to study drug following worst case principle. Missing severity of an AE will be summarized as a severe AE. Duration of the AE is classified in the '>21 Days' category if an AE is ongoing for more than 21 days by the last visit of the subject in the study.

Immunogenicity samples with a positive titer value will undergo a log transformation for analyses. Samples with titer level less than 10 will be assigned or imputed as a log transformed titer of 1 for analyses.

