8.4.1. Time Period and Frequency for Collecting AE and SAE Information

All SAEs and AEs will be collected by the investigator from the time of signing the informed consent through the Day 180 Visit or for 28 days after the last study treatment for those who terminate early. All ongoing AEs must be followed to resolution or until the Day 180 Visit or for 28 days after the subject's last study treatment visit for subjects who terminate early, whichever comes first.

All SAEs will be recorded and reported to the sponsor or designee within 24 hours, as indicated in Section 10.3. The investigator will submit any updated SAE data to the sponsor within 24 hours of it being available.

Investigators are not obligated to actively seek AEs and SAEs after conclusion of subject study participation. However, if the investigator learns of any SAE, including death, at any time after the subject has been discharged from the study, and the investigator considers the event to be reasonably related to the study treatment or study participation, the investigator must promptly notify the sponsor.

The method of recording, evaluating, and assessing causality of AEs and SAEs and the procedures for completing and submitting SAE reports are provided in Section 10.3.

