6.2. Derived Variables

Table 18 defines the derived variables for study parameters:

Table 18: Derived Variables and Definition

Variable	Definition
Age Group	18 – <35 years 35 – <45 years 45 – <60 years
Height (cm)	If height is recorded in inches, then height is equal to the recorded value multiplied by 2.54 and then rounded to 1 decimal place.
Weight (kg)	If weight is recorded in pounds, then weight is equal to the recorded value multiplied by 0.454 and then rounded to 1 decimal place.
Body Mass Index(BMI)	BMI will be computed using height measured at screening and body weight measured at respective visits as, $BMI (kg/m^2) = Weight (kg) / Height (m)^2$
Relative Day	The day of first injection of study drug will be considered as relative Day 1.
Study Day (for assessment on or after Day 1)	Study Day will be computed as: Date of Assessment – Date of Day 1 + 1
Study Day (for assessment before Day 1)	Study Day will be computed as: Date of Assessment – Date of Day 1
Baseline	Baseline is defined as the last non-missing measurement/assessment prior to the first dose of study drug. For vital signs, the baseline will be the Day 1 pre-dose values. For clinical laboratories this will be the screening value. The assessments made in unscheduled visits will be considered in calculation of baseline, if the unscheduled assessment is the closest value preceding the first dose of study drug.
Change from Baseline	Change from baseline will be derived as: post-baseline visit/time point value – the baseline value.
Last Date in Study	Last date in study is defined as: 
 • The date of Day 180 if the subject completes the study. • The date of early termination visit if the subject is terminated early from study at a non-scheduled visit. • The date of the latest scheduled visit if the subject is terminated early from study at a scheduled visit or lost to follow-up.
Age (Years) at EFP Symptom Onset	Date of EFP symptoms reported – Date of Birth/365.25. See Section 6.3.1.3 for handling of partial or unknown EFP symptom onset dates.
Time (Years) since last EFP treatment	Date of most recent EFP treatment – Date of informed consent/365.25. See Section 6.3.1.3 for handling of partial or unknown EFP treatment dates.
Baseline CR-PCSS Buttock Score	Investigator baseline CR-PCSS scores for each buttock will be based on the investigator's CR-PCSS evaluation done at the Screening Visit.

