Duration (Minutes) of Exposure at each visit	Date/Time of Last Injection – Date/Time of First Injection
Duration (Days) of AE	AE end date – AE start date + 1
AE Onset Day	AE start date – Date of first injection + 1

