7.8.2. Adverse Events

All AE summary tables will include only TEAEs, unless otherwise specified.

TEAEs will be summarized by SOC and PT. A subject will only be counted once per SOC and PT.

For TEAEs by severity grade (mild, moderate, severe), if a subject has multiple events occurring in the same SOC or same PT, then the event with the maximum intensity (ie, severe) will be counted.

For TEAEs by relationship to study drug, if a subject has multiple events occurring in the same SOC or same PT, the event with the highest association (i.e. related) to study drug will be summarized.

AEs will be presented in decreasing order of the incidence at SOC level and within each SOC, in decreasing order of the incidence at the PT level.

An overall summary of TEAEs and TEAEs related to study drug will be presented and will include:

- Total number of TEAEs reported.
- Total number of TEAEs reported by severity.
- Total number of TEAEs of special interest.
- Subjects with any TEAE.
- Subjects with any TEAE of special interest.
- Subjects with any serious TEAE.
- Subjects with any severe TEAE.
- Subjects with no severe TEAEs, but at least one moderate TEAE.
- Subjects with no severe TEAEs, but at least one mild TEAE.
- Subjects with any TEAEs leading to drug interruption/discontinuation.
- Subjects with any TEAEs leading to withdrawal from study.
- Subjects with any TEAEs resulting in death.

The following summary tables will be presented by SOC and PT:

- All TEAEs.
- TEAEs by severity.
- All study drug related TEAEs.
- Study drug related TEAEs by severity.
- Duration of study drug related TEAEs (1 – 4 days, 5 – 7 days, 8 – 14 days, 15 – 21 days and >21 days).
- TEAEs of special interest.

The most common serious and non-serious TEAEs by order of frequency (most frequent, 2nd most frequent, and 3rd most frequent) will be summarized by PT. The most common serious and non-serious AEs are those with any PT that at least 5% of the subjects reported at least once.

The following listings will be presented by subject:

- All AEs.
- Serious AEs.
- AEs resulting in drug interruption/ discontinuation.
- AEs resulting in study withdrawal.
- AEs resulting in death.
- AEs of special interest.

Refer to [Table 18](#) for computation of duration of AEs.

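### The rule for unresolved AEs in SAP 6.3 stops at the last visit, so some last-dose reactions known to exceed 21 days are not counted as such (minor point)

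*SAP*

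**What the plan says.** SAP 7.8.2 plans a table headed "Duration of study drug related TEAEs", by system organ class and preferred term, with five bands: "1 – 4 days, 5 – 7 days, 8 – 14 days, 15 – 21 days and >21 days". No band for ongoing events is listed.

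SAP Table 18 (Section 6.2) defines AE duration as "AE end date – AE start date + 1". SAP 6.3 adds one rule for unresolved events: they go to the >21-day band "if an AE is ongoing for more than 21 days by the last visit of the subject in the study". The same section states "There will be no imputation of missing values for safety data", with exceptions for missing relationship and missing severity, and says that for categorical variables "a category documenting the frequency of missing values will be displayed in the summary tables". SAP 6.1 bases percentages on subjects with non-missing values.

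Protocol 8.4.1 collects AEs "through the Day 180 Visit or for 28 days after the last study treatment for those who terminate early". In early terminators, ongoing AEs are followed to resolution or for 28 days after the last treatment visit, whichever is sooner. SAP 3.11 repeats the 28-day collection period. In SAP Table 18, one definition of the last date in study is "The date of the latest scheduled visit if the subject is terminated early from study at a scheduled visit or lost to follow-up"; that visit can be a dosing day.

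**The concern.** The protocol and the SAP use different end points for the same information. The protocol can supply AE status up to 28 days after the last treatment, but the SAP classifies an unresolved AE by its age at the last visit. If the last visit was the dosing visit, a reaction from that session is one day old on the SAP count, however long it is later seen to persist.

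Where follow-up is collected, the loss is uneven. In the same subjects a short event receives an end date and is counted in its band, while a long one receives none and is left out. SAP 6.3 assigns the worst case to missing severity and missing relationship, but gives unresolved duration only this partial protection.

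The affected figure is the share of drug-related TEAEs lasting more than 21 days. Protocol 2.2 (Background) says that AEs in previous studies often resolved within 2 to 3 weeks, so the 21-day cut is the one a reader will use to compare this study with that experience.

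**Working it through.** **Number of subjects who could be affected.** Protocol 1.1 plans 150 dosed and about 135 completing; Protocol 9.1 and SAP 3.6.1 assume about 10% dropout. 150 × (1 − 0.10) = 135, which reproduces the plan's figure and leaves 150 − 135 = 15 early terminators.

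**The rule in days.** Age at last visit = last visit day − onset day + 1. Onset is taken as the dosing day and the event is unresolved.

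| Onset | Last visit | Age by last visit | Counted as >21 days? |
|---|---|---|---|
| Day 1 | Day 22 | 22 | Yes |
| Day 22 | Day 22 | 1 | No |
| Day 22 | Day 29 | 8 | No |
| Day 22 | Day 43 | 22 | Yes |
| Day 43 | Day 43 | 1 | No |
| Day 43 | Day 57 | 15 | No |
| Day 43 | Day 90 | 48 | Yes |

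The gap therefore concerns AEs that start within about 21 days before the last visit, mainly those from the last dose. The first and fourth rows depend on the added day: without it the age is 21 and the event is not counted. SAP 6.3 does not say which count applies to ongoing events.

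**The same events at the 28-day follow-up.** Onset on the dosing day and still present 28 days later gives 28 + 1 = 29 days. Onset k days after dosing gives 28 − k + 1, which exceeds 21 for k up to 7 (28 − 7 + 1 = 22). So an AE that starts within 7 days of the last dose and is still present at the 28-day follow-up is known to have lasted more than 21 days.

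**Completers.** An AE that starts on Day 160 and is unresolved on Day 180 has age 180 − 160 + 1 = 21. It has no end date, no duration and no listed band.

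**Size.** The documents give no duration distribution, so these figures are illustrative.

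(a) *Upper-end formula.* Let p be the true share above 21 days and d the share of events that belong to early terminators. Suppose all their long events are lost and all their short events kept, with durations unrelated to dropout. The table then shows (1 − d)p / [(1 − d) + d(1 − p)], a shortfall of dp(1 − p)/(1 − dp), roughly proportional to d. With d = 10%:

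| True share | Table shows | Shortfall (points) |
|---|---|---|
| 10% | 0.09/0.99 = 9.1% | 0.9 |
| 20% | 0.18/0.98 = 18.4% | 1.6 |
| 30% | 0.27/0.97 = 27.8% | 2.2 |
| 40% | 0.36/0.96 = 37.5% | 2.5 |

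(b) *Simulation.* Three doses, onset 0 to 2 days after dosing, lognormal duration with log-SD 0.6, 10% dropout unrelated to duration. The last visit is the dosing day, a later early termination visit or the next scheduled visit, with and without the 28-day follow-up.

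| Median duration | True share >21 days | Shortfall (points) | Events unclassified |
|---|---|---|---|
| 10 days | about 11% | 0.06 to 0.19 | 0.07% to 1.7% |
| 14 days | about 25% | 0.15 to 0.35 | 0.2% to 2.2% |
| 18 days | about 40% | 0.23 to 0.53 | 0.4% to 2.5% |

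The direction is the same in every case. The simulated shortfall is smaller than in (a) because early terminators' events from previous doses are mostly resolved or already more than 21 days old at the last visit.

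**The case against.** The strongest reply is that this needs an uncommon combination: no visit after the last dose, yet AE follow-up to 28 days. Protocol 7.2 calls for early termination procedures when a subject discontinues, and Protocol 7.1 encourages discontinuers to complete the remaining visits. Table 18 allows for an early termination visit at a non-scheduled time. A visit late enough closes the gap for that subject. A subject who is truly lost has no 28-day contact, so her event is not known to be long; if her short and long events alike are unresolved at the last visit, leaving them all out adds almost no bias. Virtual safety visits, allowed during COVID-19 interruptions (Protocol 8.3), might themselves count as the last visit. The unclassified events may also appear in the missing category of SAP 6.3, all AEs are listed, and the table layouts are in SAP Module 2, which is not available here.

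Most of this stands, and it limits the size. It does not remove the defect. A missing row lies outside the percentages, and it would label as missing an event whose duration is known to exceed 21 days. A subject who withdraws consent still has AE information collected without further procedures (Protocol 7.2; SAP 4.1), so AE data can exist after the last visit.

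A reader might infer more than the documents support:

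- *That long reactions in early terminators generally go uncounted.* They do not: an event already ongoing more than 21 days at the last visit is classified correctly.
- *That the subjects between dosing sessions at the COVID-19 halt (Protocol 2.1) show how many are affected.* That is a snapshot on one date. Those subjects were allowed to continue, and the documents do not say how many left.
- *That the benefit-risk case rests on this table.* The statement on 2 to 3 weeks is in Protocol 2.2; Protocol 2.3 (Risk/Benefit Assessment) gives no duration. Duration is one of six tables by system organ class and preferred term in SAP 7.8.2 and is not among the listed safety endpoints.

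**Conclusion.** The point holds as a minor one. The SAP's cut-off at the last visit disregards AE follow-up that the protocol requires, and can leave an event known to exceed 21 days out of the >21-day band. Events ongoing 21 days or less at the last visit, including late-onset AEs in completers, have no computable duration and no listed band.

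The >21-day share is biased downward by about 0.1 to 2.5 points at the planned 10% dropout. The lower end comes from the simulation and the upper end from the formula that loses every long event in early terminators. Both rest on assumed durations and on dropout unrelated to duration. A larger bias would need subjects to leave because of long reactions; that is possible, but nothing in the documents shows it. The study is open-label and the analysis descriptive, and no decision rule uses this table.

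**What to change.** In SAP 6.3, measure ongoing AEs to the last date of AE follow-up instead of the last visit. Define that date as the latest visit, virtual contact or telephone contact, including the 28-day post-treatment follow-up for early terminators. State that the count uses the same added day as the duration formula in Table 18.

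In the SAP 7.8.2 duration table, add a row for events ongoing 21 days or less at last AE follow-up, and keep those events in the denominator, so that every drug-related TEAE falls in one row.

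The cost is two sentences and one table row, using follow-up the protocol already requires. The >21-day figure may be slightly less favourable.

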6.3.1. Imputation of Partial Dates

6.3.1.1. TEAE Status for Completely Unknown Start Date

The following rules will apply in cases where start date of an AE is completely unknown:

- If the AE onset date is unknown and the end date is on or after first injection on Day 1 or ongoing, then the AE will be considered a TEAE.
- If the AE onset date is unknown and the end date is before first injection on Day 1, then the AE will not be considered a TEAE.
- If both the start and end dates are unknown (or end date is ongoing), then the AE will be considered a TEAE, following the worst-case principle.

If the AE onset date is partly present and month/year is prior to the first injection date, then the AE will not be considered a TEAE.

6.3.1.2. Concomitant Status of Medication for Completely Unknown Start Date

The following rules will apply in cases where start date of concomitant medication is completely unknown:

- If the medication onset date is unknown and the end date is after the screening date but before the Day 180 visit date or 28 days after the last study treatment for those who terminate early or the medication is ongoing, then the medication will be considered as concomitant.
- If the medication onset date is unknown and the end date is before the screening date, then the medication will not be considered as concomitant.

- If both the start and end dates are unknown, then the medication will be considered as concomitant. This approach is considered to be the most conservative following the worst-case principle.

If the medication onset date is partly present and month/year is prior to the first injection date, then the medication will not be considered as concomitant.

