6.7. Prior and Concomitant Medications and Procedures

The start and stop date, dose, unit, frequency, route of administration, and indication for all prior (taken within the 90 days prior to the Screening Visit) and concomitant (taken from the Screening Visit through the Day 180 Visit or for 28 days after the last study treatment for those who terminate early) medications and nondrug therapies (eg, blood transfusions, oxygen supplementation, physical therapy, etc) received will be recorded.

In addition, all prior treatments for EFP will be recorded with start and stop date, dose, unit, frequency and route of administration.

The use of compression at the treatment areas is allowed during the study at the discretion of the investigator. Compression is considered a concomitant procedure and will be recorded appropriately, if used.

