4.4. Prior/Concomitant Medications

All medications will be coded using World Health Organization (WHO) Drug Dictionary, by active ingredient and WHO anatomical therapeutic chemical (ATC) classification of ingredients.

A prior medication is defined as any medication taken within the 90 days prior to the Screening Visit.

A concomitant medication is any medication taken between the Screening Visit and the Day 180 Visit or 28 days after the last study treatment for those who terminate early or the medication is reported as ongoing.

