7.6. Prior/Concomitant Medications and Procedures

Prior and concomitant medications will be summarized by cohort and overall using frequency counts and percentages by active ingredient within each ATC, with ATC and active ingredients ordered alphabetically. Prior and concomitant procedures (non-drug therapies) will be summarized by cohort and overall using frequency counts and percentages with name of the procedures ordered alphabetically. Multiple uses of the same medication/procedure by a subject will be counted only once.

A subject listing of medications indicating prior and concomitant medications and procedures will be provided. Similarly, a separate listing of medications and procedures for EFP/Cellulite will also be presented.

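### SAP 6.3.1.2 makes a medicine with a partial start date before first injection non-concomitant even if it is still being taken, which contradicts SAP 4.4 (minor, descriptive tables only)

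*SAP*

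**What the plan says.** SAP 4.4 gives the general definition: "A concomitant medication is any medication taken between the Screening Visit and the Day 180 Visit", with a limit of 28 days after the last treatment for early terminators, "or the medication is reported as ongoing". Protocol 6.7 uses the same window for recording: "concomitant (taken from the Screening Visit through the Day 180 Visit or for 28 days after the last study treatment for those who terminate early". Neither makes status depend on whether the medicine began before the first injection. SAP 4.4 also defines prior medication, as use within the 90 days before Screening.

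SAP 6.3.1.2 then deals with incomplete start dates.

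- First bullet, start wholly unknown: concomitant if "the end date is after the screening date but before the Day 180 visit date" (or within 28 days of last treatment for early terminators) "or the medication is ongoing, then the medication will be considered as concomitant".
- Second bullet, start wholly unknown and end before Screening: not concomitant.
- Third bullet: "If both the start and end dates are unknown, then the medication will be considered as concomitant". The SAP justifies this by the worst-case principle.
- Closing sentence, start partly known: "medication onset date is partly present and month/year is prior to the first injection date, then the medication will not be considered as concomitant".

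The output affected is in SAP 7.6: "Prior and concomitant medications will be summarized by cohort and overall using frequency counts and percentages by active ingredient within each ATC". A subject listing of prior and concomitant medications is also planned there.

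Two other places carry small slips. Table 18 in SAP 6.2 closes the top age group below 60, while inclusion criterion 1 admits age 60. In the TEAE overview of SAP 7.8.2, the moderate line leaves out subjects with a severe event; the mild line leaves out severe but not moderate.

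**The concern.** The closing sentence overrides the definition for the records where partial dates are most natural: long-running medicines whose start the subject remembers only as a month or a year. It also uses first injection as its reference point, whereas concomitant use is defined from Screening. A similar sentence ends SAP 6.3.1.1, where it decides whether an adverse event is treatment-emergent. First injection suits that purpose, and the medication sentence may have been modelled on it, but that is an inference.

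At stake is the accuracy of a descriptive table of background medication in an open-label safety and efficacy study, together with the concomitant label in the listing. No test, interval or efficacy endpoint uses this classification.

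**Working it through.** The documents give no figure to reproduce, so the check applies the rules to example records.

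**Ongoing medicine, three levels of knowledge about the start**

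| Start date | Rule | Status |
|---|---|---|
| Fully known, 2015 | SAP 4.4 | Concomitant |
| Wholly unknown | 6.3.1.2, first bullet | Concomitant |
| Known only as June 2015 | 6.3.1.2, closing sentence | Not concomitant |

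The medicine is the same in each row, yet the middle amount of information gives the opposite answer to both extremes.

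**Partial-date records under assumed visit dates**

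Assumed: Screening 10 Feb 2020; first injection 5 Mar 2020 (24 days later, inside the 28-day limit of Protocol 5.4); Day 180 Visit 1 Sep 2020. The 90-day prior window then opens on 12 Nov 2019. The columns for SAP 4.4 and prior status use the actual dates. The last column uses only the month and year of the start.

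| Medicine | SAP 4.4 | Prior? | 6.3.1.2 closing sentence |
|---|---|---|---|
| June 2015, ongoing | Concomitant | Yes | Not concomitant |
| 3 Feb to 1 June 2020 | Concomitant | Yes | Not concomitant |
| 20 Feb to 1 Apr 2020 | Concomitant | No | Not concomitant |
| June to Dec 2019 | Not concomitant | Yes | Not concomitant |
| From 20 Mar 2020, ongoing | Concomitant | No | Sentence does not apply |

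Rows 1 to 3 are misclassified. Rows 1 and 2 still appear as prior. Row 3, started between Screening and Day 1, appears as neither. That group is narrow: the gap is at most 28 days, and the start month can precede the injection month only if Screening and Day 1 fall in different calendar months. The closing sentence only takes concomitant status away and never grants it, so the direction of error is fixed.

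**Limits of the first bullet**

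The second bullet covers ends before Screening and the first covers ends strictly after Screening and strictly before Day 180. With the start unknown, an end date exactly on Screening or exactly on Day 180 meets neither.

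**Editorial items**

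- Age: 18–34 is 17 whole-year ages, 35–44 is 10 and 45–59 is 15; 17 + 10 + 15 = 42. Eligible ages 18–60 number 43. The one left out is 60.
- TEAE lines: there are seven possible mixes of mild, moderate and severe. Six are counted once across the three lines. Mild plus moderate without severe is counted twice: severe 0, moderate 1, mild 1, sum 2, against 1 subject with any TEAE.

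**The case against.** The strongest reply is that little is lost. A long-term medicine that loses concomitant status was normally also taken in the 90 days before Screening, so it is still summarised as prior and still listed. Repeat uses of a medicine count once per subject under SAP 7.6, so a dropped record changes the count only if the subject has no other qualifying record of it. Prohibited medication is captured separately as a protocol deviation under SAP 4.3. All of this stands. A reader might infer that medicines vanish from the report or that the table is certainly undercounted; the documents support only that it may be.

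A reader might also infer an undeclared departure from the protocol, because SAP Table 19 lists no changes. That is too strong. Protocol 6.7 says what is to be recorded and sets no partial-date rule, and Table 19 covers only significant changes. The firm contradiction is inside the SAP, between 4.4 and 6.3.1.2. The protocol window confirms which definition was intended.

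The section title speaks of wholly unknown start dates, but that is no defence: the closing sentence expressly addresses dates that are partly present, and a programmer would apply it.

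On the first bullet, the word used in SAP 4.4 for the window is not clearly inclusive, and 4.4 remains available where no bullet applies. The boundary gap is therefore a matter of tidying.

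On the editorial items, nothing in SAP 7.8.2 says that the three severity lines are exclusive or must add up, so the overlap contradicts no stated rule. The SOC/PT severity tables use maximum intensity and are unaffected. Age is also summarised as a continuous variable. The table layouts are in SAP Module 2, which was not available, so these remarks concern the SAP text alone.

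**Conclusion.** The contradiction is real, literal and minor. As written, the closing sentence of SAP 6.3.1.2 misclassifies a medicine with a partial start before first injection whenever it was still in use at or after Screening. The concomitant-medication table may be undercounted, never overcounted, by this sentence. How many records are involved cannot be told from the documents: it depends on how many partial start dates are entered. The demonstration rests on the assumed visit dates only for illustration; the conflict for an ongoing medicine holds whatever the dates.

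The primary I-GAIS endpoint, the sample size and the error rates do not depend on it. The missing age group is a true mismatch with eligibility but trivial, and may affect no subject. The overlapping TEAE lines are an ambiguity to settle, not an error against any rule in the SAP.

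**What to change.** 1. Replace the closing sentence of SAP 6.3.1.2 with a rule based on the end date: *for a partial start whose month/year precedes the first injection, the medicine is concomitant if it is ongoing, if its end date is unknown, or if it ended on or after the Screening Visit date; it is not concomitant only if it ended before Screening.* No upper limit is needed here, because a medicine begun before first injection and ended on or after Screening was necessarily used within the window.
2. In the first bullet, make both limits inclusive: on or after the Screening date, and on or before the Day 180 Visit date. Keep the limit of 28 days after last treatment for early terminators, so that the bullet matches SAP 4.4.
3. Editorial: let the top age group in Table 18 run from 45 to 60 years inclusive.
4. Editorial: if the severity lines in SAP 7.8.2 are meant to be mutually exclusive, have the mild line exclude moderate as well as severe TEAEs. If they are not, a footnote saying so is enough. Check the Module 2 layouts for the same wording.

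The cost is a few words of SAP text and the matching program code. Data collection does not change. The concomitant-medication table may become longer.
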